### 3.0 Introduction

This Statistical Analysis Plan (SAP) describes the statistical methods that will be used during the analysis and reporting of data collected under F. Hoffmann-La Roche Ltd Protocol WP40608.

This SAP should be read in conjunction with the study protocol and electronic case report form (eCRF). This version of the plan has been developed using the protocol dated 03-Jun-2018 (including all amendments up to this protocol date) and the final eCRF(s) dated 02-Jun-2018.

An approved and signed SAP is a requirement for database lock.

This SAP only covers the results that will be processed by the PRA Early Development Services (EDS) Biostatistics Department.

PRA EDS will perform the pharmacokinetic (PK) and safety and tolerability evaluation.

This SAP supersedes the statistical considerations identified in the protocol; where considerations are substantially different, they will be so identified. Any post-hoc or unplanned analyses, or significant changes from the planned analysis in this SAP performed to provide results for inclusion in the clinical study report (CSR) but not included in this SAP, will be clearly identified in Section 9.8.2 of the CSR. Changes to planned analyses do not require an updated SAP but should be included in the CSR if significant.

### 4.0 Changes from Previous Version of Approved SAP

This is the first version of the SAP.

### 5.0 Study Objectives

This study will investigate the effect of rifampicin treatment on the PK of balovaptan and its major metabolites M2 and M3.

#### 5.1 Primary Objective

To investigate the effect of multiple doses of rifampicin, a potent cytochrome P450 (CYP)3A4 inducer, on the PK of balovaptan 10 mg once daily (qd) and its major metabolites M2 and M3 at steady state in healthy subjects.

##### 5.1.1 Primary Endpoints

PK parameters for balovaptan, M2, and M3 following 10 days of qd dosing of balovaptan 10 mg:

- Maximum observed plasma concentration (Cmax)
- Area under the plasma concentration curve from time 0 to 24 hours (AUC0-24h)

#### 5.2 Secondary Objectives

- To evaluate the safety and tolerability of balovaptan 10 mg qd administered alone and in combination with rifampicin in healthy subjects.
- To investigate the effect of multiple doses of rifampicin on secondary PK parameters of multiple doses of balovaptan 10 mg qd and its major metabolites M2 and M3 at steady state in healthy subjects.

##### 5.2.1 Secondary Endpoints

Safety and tolerability:

- Adverse events (AEs)
- Clinical laboratory values

- Vital signs
- Electrocardiogram (ECG)
- Columbia-Suicide Severity Scale (C-SSRS)
- Physical examination

Secondary PK parameters for balovaptan and metabolite M2 and M3:

- Time to maximum observed plasma concentration ( $t_{max}$ )
- Metabolite to parent ratio
- Any other parameter as appropriate (see Table 1)

### 5.3 Tertiary/ Exploratory Objectives

To evaluate the plasma exposure of rifampicin 600 mg qd.

To investigate the relationship between the CYP3A4 genotype and steady state balovaptan exposure, and the influence of the CYP3A4 genotype on the effect of rifampicin on balovaptan PK. The relationship between other genotypes and PK of balovaptan may also be explored.

#### 5.3.1 Tertiary/Exploratory Endpoints

Exploratory PK parameters for rifampicin following 6 and 16 days of qd dosing:

- $C_{max}$
- AUC0-24h
- $t_{max}$
- AUC0-last
- any other parameter as appropriate (see Table 1)

The pharmacogenetics of metabolizing enzymes, transferases, transporters, etc, possibly involved in the absorption, distribution, metabolism and excretion of balovaptan and its major metabolites (e.g., CYP3A and P-glycoprotein). Results may be pooled with data from other studies of balovaptan.

## 6.0 Study Design

This study will be a single-center, non-randomized, open-label, one-sequence, two-period, within-subject study to investigate the effects of multiple doses of rifampicin on the PK and safety of multiple doses of balovaptan in healthy subjects. The study will be conducted at 1 site in the Netherlands.

Screening will be conducted up to 3 weeks prior to admission in the clinical research unit (CRU). Subjects will be in the CRU for 2 study periods. In both periods, subjects will be admitted on Day -1 (the day before dosing begins); Day 1 will be the first day of dosing. In Period 1, subjects will be discharged on Day 11 after the last assessment is completed. There will be a minimum of a 14-day to a maximum of a 21-day washout between the last dose in Period 1 and the first dose in Period 2. Subjects will therefore return to the CRU on Day 24 or up to Day 30 of Period 1 (Day -1 of Period 2) to begin Period 2. In Period 2, subjects will be discharged on Day 17 after all assessments have been performed. Subjects will return for a follow-up visit between 14 to 21 days after the last dose.

Subjects will receive the following study drugs in the 2 study periods, after an overnight fast of at least 8 hours:

#### Study Period 1:

[figure not shown]
- Days 1 to 10: oral balovaptan 10 mg qd
- Days 11 to 23 (or up to Day 30): no study drug

#### Study Period 2:

- Days 1 to 6: rifampicin 600 mg qd
- Days 7 to 16: balovaptan 10 mg qd + rifampicin 600 mg qd

Figure 1 presents an overview of the study design.

**Figure 1: Study Schema**

Abbreviations: PK = pharmacokinetic; qd = once daily;

aFull balovaptan PK profile on Day 10/11 of Period 1 and Day 16/17 of Period 2; trough concentrations on other days. Full rifampicin PK profile on Days 6/7 and 16/17 of Period 2

A total of 16 subjects will be enrolled to ensure 12 evaluable subjects.

## 6.1 Sample Size Considerations

This is an exploratory study for which no formal statistical hypothesis will be tested. Therefore, the sample size is chosen to estimate with sufficient precision the effect of CYP3A4 induction on balovaptan.

The sample size of 12 evaluable subjects was chosen based on balovaptan within-subject variability (CV%) of around 39% for AUC0-24h and 36% for Cmax as obtained from the 12 mg repeat dose in study BP25694. Based on the higher value of 39%, it was estimated that with 12 subjects the half-width of the 90% confidence interval (CI) for the ratio of treatment geometric means of the combination (balovaptan + rifampicin) versus balovaptan alone would be obtained by dividing/multiplying the ratio estimate by a factor of 1.30.

## 6.2 Randomization

Not applicable, this is a non-randomized study.

## 7.0 Overview of Planned Analysis

### 7.1 Changes from Protocol

There are no changes from the protocol.

## 7.2 Interim Analysis and Key Results

No interim reporting is planned for this study.

## 7.3 Final Analysis

Draft TFLs will be provided with the draft CSR. After Sponsor comments have been incorporated, the TFLs will be finalized and incorporated in the final CSR.

## 8.0 Data Review

### 8.1 Data Management

Data handling, transfer and coding will take place under the PRA Data Management Plan for the study.

### 8.2 Acceptance of Data for Summarization

Programming of analysis datasets and TFLs may be ongoing during the data management of the study. However, programming of analysis datasets and TFLs will be completed and quality controlled (QC'd) after database lock. Only quality assured (QA'd) results released by the Safety Laboratory, Bioanalytical Laboratory, or other external data source will be used for the programming of analysis datasets and TFLs for the final report. Any data values requiring investigation or corrections that are identified while programming the analysis datasets and TFLs will be sent to the project Data Manager. If the issue affects the TFLs the Programmer or Statistician who identified the issue will follow it to resolution.

## 9.0 Definitions and General Analysis Methods

### 9.1 Analysis Data Presentation

#### 9.1.1 Rounding

In listings, all data (except the PK data) will be presented with the same precision as the original data. Derived data will be rounded for presentation purposes.

For descriptive statistics of safety data, range values will be presented with the same precision (number of decimals or significant digits) as the data they are calculated from, median, arithmetic mean values with 1 more decimal digit, standard deviation (SD) with 2 more decimal digits. Percentages will be rounded to integers.

For the derived PK parameters Appendix 2 of the Roche Clinical Pharmacology Guideline will be followed [3]. For all PK parameters except  $t_{max}$ ; individual subject data, range values, median, arithmetic mean, geometric mean and standard deviation (SD) will be presented with a precision of 3 significant digits. The coefficients of variation (CV) with 1 decimal digit.

All individual data and descriptive statistics for  $t_{max}$  will be reported with 2 decimals, except for the CVs which will be presented with 1 decimal digit.

#### 9.1.2 Imputation

Except for the substitution of any PK concentrations below the lower limit of quantification (LLOQ) (see Section 16.2) and missing start or end date/times of Adverse Events (AEs) for the calculation of onset and duration (see Section 17.1.1), any missing data will not be imputed.

#### 9.1.3 Descriptive Statistics

Unless otherwise indicated, continuous variables will be summarized with the following descriptive statistics:

- n (number of observations),

- nmiss (number of missing observations),
- (arithmetic) mean,
- SD,
- minimum (min) value,
- median, and
- maximum (max) value.

Categorical data will be summarized with frequencies and percentages. Percentages by categories will be based on the number of subjects exposed within a treatment.

For categorical data the categories will be presented in the tables exactly as they appear in the CRF / Database.

### 9.1.4 Pooling

Summary statistics will be calculated by treatment (and time point, if applicable).

### 9.1.5 Unscheduled Measurements

Unscheduled measurements will be included in the listings. Except for unscheduled measurements used for baseline, unscheduled measurements will be excluded from the descriptive statistics and statistical analysis.

## 9.2 Analysis Data Definitions

### 9.2.1 Baseline Definition

Unless otherwise stated, baseline for post-dose evaluations within each period is defined as the last observation recorded before the first study drug administration in each period. The last observation can be an unscheduled / repeated measurement. Baseline for Electrocardiograms (ECGs) is derived as the mean of the triplicate pre-dose measurements of pre-dose assessments taken in Analysis Period 1.

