### 9.2.2 Treatment Grouping

Period will refer to the analysis (treatment) period, as opposed to study period. This means that Study Period 2 will be divided in two analysis periods, Analysis Period 2 (Days -1 to 6) and Analysis Period 3 (Days 7 to 16). The study will therefore consist of 3 analysis periods. For Analysis Period 3, the analysis day will also be adjusted by subtracting 6 from the study day. Thus, Period 3 will have Analysis Days 1 to 10.

Label	Grouping
Analysis Period	
Study Drug	Balovaptan (reference), rifampicin, balovaptan + rifampicin (test)
Treatment	Treatment S: 10 mg balovaptan Treatment I: 600 mg rifampicin Treatment S+I: 10 mg balovaptan + 600 mg rifampicin

S= Substrate, I= Index Inducer

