### 9.2.3 Common Variable Derivations

Variable	Data Type	Definition/Calculation	Note
Change from Baseline	All	Post-dose Observation minus Baseline Observation	
Analysis Period	All	Time period starting 1 day before dosing of each of the treatments and ends 1 day before dosing in next analysis period or at the start of the follow-up period for the last treatment.	
Analysis Study Day (Prior to Dose)	All	Date of Measurement minus Dose Date	
Analysis Study Day (Post Dose)	All	Date of Measurement minus Dose Date +1	

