  - b A standardized breakfast will be provided at least 30 minutes after dosing of balovaptan alone, rifampicin alone, or balovaptan + rifampicin together in either period. A standardized lunch and standardized dinner will be provided 4 and 10 hours post dose, respectively, in both periods. Standardized afternoon and evening snacks will be provided as well.
  - c Samples to measure the concentration of balovaptan, M2, and M3 (one sample per time point to measure all 3 analytes) will be taken at predose, and 0.5, 1, 1.5, 2, 2.5, 3, 4, 6, 8, 12, 16, 24, hours post dose on Days 10/11 of Period 1 (16- and 24-hour samples are on the morning of Day 11) and 16/17 of Period 2 (16- and 24-hour samples are on the morning of Day 17). A predose sample to measure the concentration of balovaptan, M2, and M3 will also be taken on Days 2, 4, 8, and 9 in Period 1, and on Days 8, 10, 14, and 15 in Period 2 (see also [Appendix 2](#)).
  - d Samples to measure the concentration of rifampicin will be taken predose and at 1, 1.5, 2, 3, 4, 6, 12, and 24 hours post dose of rifampicin on Days 6/7 and 16/17 of Period 2 (24-hour samples are on the morning of Days 7 and 17) (see also [Appendix 2](#)).
  - e Includes measurement of height, weight and BMI.
  - f Includes measurement of weight.
  - g Triplicate ECGs will be collected as follows: in Period 1, on Day -1 and predose and 3 hours after dosing of balovaptan on Days 3, 7, and 10 and in the morning of Day 11; and in Period 2, on Day -1, and predose and 3 hours post dose on Days 3, 6, 9, 13, and 16; in the morning of Day 17, and at Follow-up (see also [Appendix 2](#)).
  - h Vital signs will be collected as follows: in Period 1, on Day -1 and predose and 3 hours after dosing of balovaptan on Days 3, 7, and 10 and in the morning of Day 11; and in Period 2, on Day -1, and predose and 3 hours post dose on Days 3, 6, 9, 13, and 16; in the morning of Day 17, and at Follow-up (see also [Appendix 2](#)).
  - i Includes measurement of body temperature.
  - j Hematology and chemistry at Screening and on Days -1 and 11 of Period 1 and on Days -1, 3, 6, 9, 13, 17 in Period 2, and follow up. Urinalysis at Screening and on Days -1 and 11 of Period 1 and on Days -1 and 17 in Period 2 and at Follow-up.
  - k For females only: FSH and serum pregnancy test at Screening, and serum pregnancy test only at all other time points.

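### For hematology, chemistry, blood pressure and pulse rate, change from baseline on the combination starts from an on-rifampicin value but on balovaptan alone from a drug-free one, and the SAP does not require the tables to say so

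*SAP*

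**What the plan says.** The default rule in SAP 9.2.1 is that "baseline for post-dose evaluations within each period is defined as the last observation recorded before the first study drug administration in each period". An unscheduled or repeated value may serve. ECG is the one stated exception: its baseline comes from pre-dose triplicates in Analysis Period 1.

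SAP 9.2.2 fixes the term: "Period will refer to the analysis (treatment) period, as opposed to study period". It splits Study Period 2 into "Analysis Period 2 (Days -1 to 6) and Analysis Period 3 (Days 7 to 16"), that is, rifampicin alone (I) and then the combination (S+I). SAP 9.2.3 bounds an analysis period differently: "Time period starting 1 day before dosing of each of the treatments and ends 1 day before dosing in next analysis period".

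The footnotes to SAP Appendix 2 give the visits in Study Period 2:
- Hematology and chemistry (footnote j): "on Days -1, 3, 6, 9, 13, 17 in Period 2".
- Vital signs (footnote h): "in Period 2, on Day -1, and predose and 3 hours post dose on Days 3, 6, 9, 13, and 16", and then the morning of Day 17.
- Urinalysis (footnote j): "Urinalysis at Screening and on Days -1 and 11 of Period 1 and on Days -1 and 17 in Period 2".
- Body temperature (footnote i, "Includes measurement of body temperature"): in the Period 2 columns of the grid the mark stands at Days -1, 16 and 17, not at Day 6.

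SAP 17.1.3 and 17.1.4 summarize results and changes from baseline by treatment and scheduled time. Neither section, nor the table titles in SAP Appendix 4, names the reference value. SAP 9.5 supplies no table shells, takes treatment labels from 9.2.2, and leaves layout to the contract research organization's standards.

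**The concern.** A secondary objective is the safety of balovaptan alone and in combination with rifampicin, and SAP 9.2.2 designates these two treatments as reference and test. A reader will set the S and S+I change columns against each other. The S column answers: how far from a drug-free state? The S+I column, for four measures, answers a different question: how far from a state already on rifampicin?

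The difference bears on expected effects. Protocol 3.3.2.2 names thrombocytopenia and raised liver enzymes among the common adverse effects of rifampicin, and both appear in hematology or chemistry. A change that arises during the six days of rifampicin alone and persists would be close to zero in the S+I change column, beside an S column that starts from no drug at all.

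**Working it through.** The plan gives no figure to reproduce here. The check applies the baseline rule to the schedule.

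**Step 1: which value becomes the baseline.** Take the last scheduled value before the first dose of the analysis period and count the rifampicin doses before it. Rifampicin is given alone on Days 1 to 6; the combination starts on Day 7.

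| Measure | S+I reference | Rifampicin doses before it | S reference |
|---|---|---|---|
| Blood pressure, pulse rate | Day 6, 3 h post dose | 6 | Day -1, Study Period 1 (no drug) |
| Hematology, chemistry | Day 6, draw time not given | 5 if predose, 6 if later | Day -1, Study Period 1 (no drug) |
| Urinalysis, body temperature | Day -1, Study Period 2 | 0 | Day -1, Study Period 1 (no drug) |
| ECG | Analysis Period 1, by exception | 0 | Analysis Period 1 |

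Reading period as study period would put the first two rows at Day -1 of Study Period 2, but SAP 9.2.2 rules that out.

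**Step 2: the Day 7 marks.** The grid in SAP Appendix 2, as it can be read, also marks Day 7 for hematology, chemistry and vital signs. Footnotes h and j and SAP Appendix 3 do not list Day 7. The balovaptan dosing row of the same grid looks displaced (it marks Day 6 and not Day 16), so a fault in reading the table is likely. If a Day 7 predose value did exist, it would follow 6 rifampicin doses and the conclusion would be the same.

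**Step 3: how many S+I changes are affected.**
- Hematology and chemistry: Days 9, 13 and 17 = 3 of 3.
- Blood pressure and pulse rate: 3 days (9, 13, 16) × 2 readings + Day 17 = 7 of 7.

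These counts place Day 17 in the combination period, as SAP 9.2.3 does. If the Day 16 limit in 9.2.2 governs, they become 2 of 2 and 6 of 6, which is still all of them.

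**Step 4: is Day -1 of Study Period 2 usable as a drug-free reference?** With the minimum 14-day washout, Day -1 falls at least 13 days after the last balovaptan dose. 13 × 24 = 312 h. With the 46 h half-life in Protocol 1.2.1.1, 312 / 46 = 6.78 half-lives, and 0.5^6.78 = 0.009, so about 0.9% of parent drug remains. Half-lives of M2 and M3 are not given.

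**Step 5: can the reader rebuild the missing change?** Invented ALT values, for illustration only.

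One subject with 20 on Day -1, 60 on Day 6 and 60 on Day 17: the S+I change is 60 − 60 = 0; from Day -1 it is 60 − 20 = +40.

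Three subjects (Day -1/Day 6/Day 17) with 20/60/30, 20/20/45 and 20/20/20:

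| Change | Values | Mean | SD | Median | Max |
|---|---|---|---|---|---|
| I: Day 6 − Day -1 | 40, 0, 0 | 13.3 | 23.1 | 0 | 40 |
| S+I: Day 17 − Day 6 | −30, 25, 0 | −1.7 | 27.5 | 0 | 25 |
| Day 17 − Day -1 | 10, 25, 0 | 11.7 | 12.6 | 10 | 25 |

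The mean is recoverable when the same subjects contribute to both columns (13.3 − 1.7 = 11.7, from unrounded values). The SD, median, minimum and maximum, which SAP 9.1.3 also plans, do not follow from the two planned columns.

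**The case against.** The strongest reply is that this is a deliberate choice. SAP 9.2.2 splits Study Period 2 on purpose, and a baseline per analysis period isolates what balovaptan adds to rifampicin. SAP 17.1.1 uses the same logic when it assigns an adverse event to the period in which it starts. The run-in effect is reported under I. This stands, and a reader who infers that the baseline rule is an error goes further than the documents allow.

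The reply also limits the consequence. Observed values are summarized by treatment and time, all laboratory data and the out-of-range values are listed, and analysis datasets are delivered. With 16 subjects planned, anyone holding the listings can compute the other change. A reader might infer that the plan hides a rifampicin effect or loses data; it does neither. The adverse event tables and the primary PK analysis are untouched.

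Two further inferences go too far. One is that a single S+I table mixes three reference states. SAP Appendix 4 keeps hematology, chemistry, urinalysis, vital signs and ECG in separate tables; only the vital signs table mixes references, because of body temperature. The other is that the tables will carry no label. The layout standards are not in the documents and nothing forbids a footnote; the SAP simply does not require one.

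What the reply does not answer is that S and S+I changes, summarized by treatment for a stated safety objective, start from different states, and no planned column gives S+I relative to no drug for these four measures.

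**Conclusion.** The point holds as a cheap improvement to a derived column and its labelling. For hematology, chemistry, blood pressure and pulse rate, every scheduled S+I change (3 and 7 time points) is taken from an on-rifampicin value, while the S changes are taken from a drug-free one. The size of any masked shift cannot be stated from the documents; the ALT values only show how it would arise.

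The conclusion assumes that the footnotes and SAP Appendix 3 govern the visit days and that no unscheduled value replaces the Day 6 one. An unscheduled value between Day 6 and the Day 7 dose would also be on rifampicin. The body temperature row rests on where footnote i stands in the grid, which is less secure.

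Two minor ambiguities sit beside this. A reader might infer that the ECG baseline is certainly Day -1 of Study Period 1, the only scheduled in-house ECG before the first dose. The documents do not settle it: the schedule uses the term predose for Days 3, 7 and 10 and describes Day -1 as prior to admission. And SAP 9.2.2 places Day 6 in Analysis Period 2, while 9.2.3 starts Analysis Period 3 one day before its first dose, which is also Day 6. The baseline value is the same either way.

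**What to change.** For hematology, chemistry, blood pressure and pulse rate in Analysis Period 3, report the change from Day -1 of Study Period 2 beside the existing change from the last value before the Day 7 dose. State the reference value in every safety table; urinalysis, body temperature and ECG need only a footnote. In one line each, say which Analysis Period 1 visit supplies the ECG baseline, and reconcile SAP 9.2.2 with 9.2.3 on the period to which Day 6 belongs.

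The cost is some SAP wording and one extra change column for four measures. All Day -1 values are already scheduled, and the incremental view is kept. The downside is slightly longer tables with two references to explain.

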1.2.1.1 Clinical Pharmacology

Exposure of balovaptan increased in a greater than dose-proportional manner following single doses of 0.5 to 76 mg, whereas an approximately linear increase in exposure was observed after repeated dosing with 12 to 52 mg once daily (qd) for 14 days.

Balovaptan was rapidly absorbed with a median time to maximum observed plasma concentration (t_{max}) between 1 and 4.5 hours after administration of single doses and between 3 and 4 hours following multiple dosing. Steady state was achieved after approximately 7 days; the mean apparent elimination half-life after the last dose (Day 14) was approximately 46 hours. Food had no relevant effect on the PK of balovaptan.

In the human mass balance study (Study BP29279), an almost complete absorption of the study drug was observed within the first 72 hours following administration.

In plasma, steady state exposure to the [REDACTED] M3 was similar to or slightly higher than that of balovaptan and exposure to the [REDACTED] M2 was lower than that of parent. M3 and M2 qualify as major metabolites in plasma.

[REDACTED]

Renal excretion was found to be the major pathway of elimination (approximately 53% of the material recovered, mostly composed of metabolites) with the primary route of

excretion via metabolism to M1 into urine, accounting for approximately 23% of the dose. A further 30% of the administered dose was recovered in feces. The majority of excretion occurred within the first 7 days.

There was no clinically/statistically relevant PK interaction with the P-glycoprotein substrate risperidone, one of only 2 approved medications for ASD symptoms in the US, and fluoxetine, a weak CYP3A4 inhibitor often used to treat associated symptoms of ASD. Administration of a single dose of balovaptan 12 mg in combination with itraconazole, a strong CYP3A4 inhibitor, resulted in an increase in the exposure of balovaptan by 36% for maximum observed plasma concentration (C_{max}) and an approximately 3.1-fold increase for area under the concentration curve from time 0 to 120 hours (AUC_{0-120h}).

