### 17.1.5 Electrocardiograms

All ECG parameters (including changes from baseline) and the corresponding abnormalities and physician's conclusions will be listed by subject.

The observed measurements for all ECG parameters (including T-wave, U-wave) and the corresponding abnormalities will be listed for all time points. The means of triplicate measurements for continuous parameters and the change from baseline of the mean triplicate measurements at each scheduled time point will be listed by subject.

Descriptive statistics will be provided to summarize mean continuous ECG parameters (observed and changes from baseline) by treatment and scheduled time. A frequency table will be provided as well to summarize the ECG parameters by physicians conclusion (normal, abnormal not clinically significant, abnormal clinically significant).

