### Appendix 3: Schedule of PK, ECG and VS Measurements

Procedure Study Day	Predose or Prior to Admission/Discharge	Hours post dose a											
		0.5	1	1.5	2	2.5	3	4	6	8	12	16	24
Blood sampling balovaptan, M2, and M3 (one sample for all 3 analytes)													
Period 1													
Days 2, 4, 8, and 9	X b												
Day 10	X b	X	X	X	X	X	X	X	X	X	X	X	X c
Period 2													
Days 8, 10, 14, and 15	X b												
Day 16	X b	X	X	X	X	X	X	X	X	X	X	X	X d
Blood sampling rifampicin													
Period 2													
Day 6	X b		X	X	X		X	X	X		X		X e
Day 16	X b		X	X	X		X	X	X		X		X d
12-lead electrocardiograms													
Period 1													
Day -1 and Day 11	X f												
Days 3, 7, and 10	X b						X						
Period 2													
Day -1 and Day 17	X f												
Days 3, 6, 9, 13, and 16	X b						X						
Vital signs													
Period 1													
Day -1 and Day 11	X f												
Days 3, 7, and 10	X b						X						
Period 2													
Day -1 and Day 17	X f												
Days 3, 6, 9, 13, and 16	X b						X						

aFor sampling to measure balovaptan, M2, and M3, and for ECG and vital signs measurements on days balovaptan or balovaptan together with rifampicin are administered, post dose is relative to time of balovaptan dosing; for sampling to measure rifampicin and for ECG and vital signs measurements on days balovaptan is not administered, post dose is relative to time of rifampicin dosing

b10 minutes predose (or time matched, when not dosed)

cDay 11

dDay 17

eDay 7

fPrior to admission or discharge

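### The SAP's ECG baseline sentence is ambiguous and admits on-treatment troughs from Days 3, 7 and 10; it should name the drug-free Day -1 triplicate

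*SAP*

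**What the plan says.** SAP 9.2.1 first sets a general rule: baseline "is defined as the last observation recorded before the first study drug administration in each period". It then treats ECGs separately: "Baseline for Electrocardiograms (ECGs) is derived as the mean of the triplicate pre-dose measurements of pre-dose assessments taken in Analysis Period 1". The ECG sentence names no study day and uses the plural for the assessments. It is the only ECG baseline given, so it appears to serve all three analysis periods.

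SAP Appendix 2, footnote g, schedules ECGs "in Period 1, on Day -1 and predose and 3 hours after dosing of balovaptan on Days 3, 7, and 10", and again on the morning of Day 11. Protocol Appendix 1 has the same footnote. SAP Appendix 3 times the first ECG on Days 3, 7 and 10 at ten minutes before the dose, but labels the Day -1 and Day 11 ECGs "Prior to admission or discharge". Dosing in Study Period 1 (SAP 6.0) is "Days 1 to 10: oral balovaptan 10 mg qd".

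SAP 17.1.5 states how the baseline is used: "Descriptive statistics will be provided to summarize mean continuous ECG parameters (observed and changes from baseline) by treatment and scheduled time". Individual changes at each scheduled time point are also listed.

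**The concern.** A programmer who selects the ECGs labelled predose in Analysis Period 1 obtains Days 3, 7 and 10, perhaps with Day -1 added. All three are taken during daily balovaptan dosing. Any ECG effect already present at trough would enter the baseline and be subtracted from every later change.

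ECG is a named secondary safety endpoint (SAP 5.2.1). Arrhythmia, syncope and palpitations are among the adverse events of special interest (Protocol 5.2.3), and the protocol's table of contents lists cardiac toxicity among the potential important risks of balovaptan. A change score that can absorb part of the drug's own effect is a poor safety summary. Little in the SAP would catch a wrong choice: no table shells are provided (9.5), and the ECG dataset is not among those classed as critical and double programmed (9.2.4.1).

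**Working it through.** The plan gives no figure for this point, so there is none to reproduce.

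**Step 1: which Period 1 ECGs can be baseline?**

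| ECG | Label in SAP Appendix 3 | Balovaptan doses already taken |
|---|---|---|
| Day -1 | prior to admission | 0 |
| Day 3, first | predose | 2 |
| Day 7, first | predose | 6 |
| Day 10, first | predose | 9 |

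Three readings are possible: (A) the three troughs only; (B) Day -1 pooled with the three troughs; (C) Day -1 only.

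**Step 2: a consequence that needs no PK model.** Under A, a subject's changes at the Day 3, 7 and 10 predose points are deviations from their own mean. With all three recorded they sum to zero, whatever the drug does. Under B the four changes sum to zero.

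**Step 3: size, under assumptions.** Inputs from Protocol 1.2.1.1: "the mean apparent elimination half-life after the last dose (Day 14) was approximately 46 hours", and a multiple-dose tmax of 3 to 4 hours. Assumptions of this check: a one-compartment model with first-order absorption, and ECG effect proportional to balovaptan concentration.

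- ke = ln 2 / 46 = 0.0151 per hour.
- ka is solved from the steady-state relation tmax = ln{ka(1 − e^(−24ke)) / [ke(1 − e^(−24ka))]} / (ka − ke). This gives 1.024 per hour for tmax 3 h and 0.663 for tmax 4 h.
- C(t) = sum over doses given of ka/(ka − ke) × [e^(−ke·s) − e^(−ka·s)], where s is the time since that dose. Units are arbitrary.

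| | tmax 3 h | tmax 4 h |
|---|---|---|
| Predose, Day 3 | 1.202 | 1.212 |
| Predose, Day 7 | 2.069 | 2.086 |
| Predose, Day 10 | 2.245 | 2.264 |
| 3 h post dose, Day 10 | 3.064 | 2.996 |

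Share of the Day 10 3-hour effect that is subtracted:

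- A: (1.202 + 2.069 + 2.245)/3 = 1.839, and 1.839/3.064 = 0.60. For tmax 4 h: 1.854/2.996 = 0.62.
- B, with zero for Day -1: 5.516/4 = 1.379, and 1.379/3.064 = 0.45. For tmax 4 h: 1.391/2.996 = 0.46.
- C: 0.

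With the half-life varied from 24 to 60 hours (tmax 3 to 4 h), A runs from about 52% to 62% and B from about 39% to 47%.

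**Step 4: the other treatments.** The shortest washout is 14 × 24 = 336 hours, or 336/46 = 7.3 half-lives, which leaves about 0.6% of the balovaptan. The rifampicin-alone ECGs are therefore nearly balovaptan-free. Under A, a treatment with no ECG effect would show a change of about −0.60 times the Day 10 balovaptan effect; under B, about −0.45 times.

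With one baseline b per subject, however, (balovaptan − b) − (rifampicin − b) = balovaptan − rifampicin. Within-subject differences between treatments do not depend on b.

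**The case against.** The strongest reply is that Day -1 was meant all along. SAP 9.2.3 starts each analysis period one day before dosing, so Day -1 lies inside Analysis Period 1. SAP Appendix 3 puts the Day -1 ECG in a column shared by predose and admission records. SAP 17.1.1 uses the term pre-dose for adverse events before any drug, and Protocol 4.1.2 speaks of a predose baseline ECG for eligibility. The ECG sentence may only mean to average the triplicate and to use Period 1 for every period. This stands as a plausible reading, under which nothing is lost. It does not settle the matter: the sentence omits the first-dose anchor, its plural sits poorly with one visit, and the schedule reserves the predose label for Days 3, 7 and 10.

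The size can also be challenged. The documents give no relation between concentration and ECG. Protocol 3.3.2.1 describes the multiple-dose PK as time-dependent, so a linear model is only approximate. The text of the cardiac-toxicity section is redacted, so the nature of that risk cannot be judged. These limits stand, and the percentages are illustrations.

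The reach is narrow too. Observed ECG values are listed and summarised, and physician conclusions are tabulated, without any baseline. No hypothesis is tested (SAP 9.4.3). Protocol 6.5 asks only for ECG listings with abnormalities flagged.

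**Conclusion.** The definition is ambiguous in a way that matters: followed by the schedule's own labels, it gives an on-treatment ECG baseline. On the trough-only and pooled readings, the descriptive changes from baseline understate a balovaptan effect that is present at trough, and move the rifampicin-alone and combination changes by the same amount. Under proportionality, a 46-hour half-life and tmax of 3 to 4 hours, the loss at Day 10, 3 hours, is about 60% for troughs only, about 45% with Day -1 pooled and 0% for Day -1 alone.

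A reader might infer that the plan certainly uses an on-treatment baseline, that most of any effect is cancelled, or that treatment comparisons are biased. The documents do not support these. Day -1 remains a possible reading, the pooled reading removes less than half at Day 10, and a common baseline drops out of within-subject differences. The primary PK analysis is untouched. This should be fixed, but it is not a critical flaw.

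**What to change.** Replace the ECG sentence in SAP 9.2.1 with:

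> For all analysis periods, the ECG baseline is the mean of the last triplicate taken before any study drug is given in Study Period 1 (scheduled: Day -1). The predose ECGs on Days 3, 7 and 10 are on-treatment, do not form part of baseline, and are summarised as post-baseline time points.

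Carry the same rule into the ECG analysis dataset specification before database lock. It uses data already scheduled and keeps one common baseline. If Day -1 was always intended, no result changes. The cost is a slightly noisier baseline, because it rests on one triplicate rather than an average over several days.
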